#### Study enrolment:

Parents will be approached while their child is receiving initial asthma therapy in the Emergency Room of the Post Graduate Institute of Paediatric Medical Research in Chandigarh, India. Parents will be approached by one of the two local study coordinators (both are qualified paediatricians), during the child's 2 hour observation period in the Emergency Department. At that time parents will be given the invitation letter, written in local language (Hindi) and the research coordinator will answer any questions they have. If they cannot read, the information will be read to them in a private room. If the child fails to improve and requires hospital admission, consent for study participation will be sought once the decision to admit has been made. This will not delay treatment in any way. Children will only be eligible to enroll in the study whilst they are in the Emergency

department. Previously admitted ward patients are not eligible. All study information and consent documents are attached in section 9.

## Randomization:

Once consent has been obtained, treatment selection will be decided using consecutively numbered envelopes randomized in groups of six. These envelopes will be stored in a box in the Emergency Department. Once consent has been obtained, an envelope will be selected in numerical sequence to determine the child's allocated treatment group. The envelope will then be stapled to the consent form to enable the investigator to know each patient's subject study number.

## Safety Monitoring:

Although there are decades of experience confirming the safety of NIV in children, this study represents a significant change to well-established conventional therapy so extra levels of observation of the treatment groups have been included in the study design:

- The study hospital has agreed to set aside a 3 bed ward dedicated to the duration of the study. It will be staffed by 4 nurses and 2 qualified pediatricians who will provide continuous 24 hr a day coverage for the study participants. Staff salaries for the study will be covered by study funds.
- Since this is an open study, we plan to perform an interim review of adverse events after 10 patients have been enrolled in each treatment arm. The clinical reviewer will be [name] and the statistical reviewer will be [name] both from Children's Hospital, Vancouver.
- The head of ER at PGIMER, Chandigarh, has agreed to be the local external monitor. The research coordinators will be the most likely people to pick up adverse events. All RCs will be trained in the study protocol, including the reporting process in the event of an adverse event. Nursing staff are also aware of the need for extra monitoring and the need to report potential problems.

## Sample size calculation.

In order to have an impact on common practice, we would define a significant treatment effect as a 25% reduction in time to PRAM of 3. In order to demonstrate this effect with a power of 80% and a 5% chance of a type 1 error, we need an estimate of mean time to PRAM of 3 plus standard deviation from previous published work. Unfortunately, there is very little published information to act as a guide. The only published pediatric study that provides relevant data is a pilot study by Basnet et al.[17] Using only 10 patients in each arm, they showed BiPAP reduced time in ICU (48+/- 16 hrs vs. 36+/-14 hrs). They used a clinical score to guide management but it was different to the PRAM. If we take the higher of these standard deviations as a rough guide to the average ICU admission time and combine it with a power of 80% and type 1 error risk of 5%, we will need 26 patients in each arm to detect a 25% reduction in time to PRAM of 3. It must be emphasized that the shortage of relevant literature makes this only a rough estimate.

Statistical analysis.

Outcomes in the two treatment arms of the study (BiPAP and CPAP), will be compared to those in the control group (conventional acute paediatric asthma treatment). The principal end points will be analysed in the following ways:

1. Changes in asthma score over time.

The PRAM respiratory distres score is based on objective and subjective observations so the final values are non-parametric. Multiple comparisons over time, between treatment group and control, will be made with the Kruskal-Wallace test with Dunn's posthoc test.

2. Time to reach asthma score <3.

The value will be measured in hours after starting treatment so the values will be parametric. Comparison between treatment and control values will be made using t test. 3. Total number of pharmacological treatments per day.

The total number of drug treatments will be calculated for each 12 hour period. These are parametric values. Comparisons between control and treated group of repeat measures over time, will be made by analysis of variance with Tukey's post-hoc test. 4. Lung function tests.

Standard spirometry and flow-volume loops will be performed with portable equipment in children old enough to cooperate. The main measured end point for analysis will be the change in Forced Expiratory Volume in 1 second (FEV1) over time. These values are parametric. Multiple comparisons between control and treated groups will be made by analysis of variance with Tukey's post-hoc test.

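### Time to the PRAM target is tested for BiPAP and CPAP against one shared control by plain t tests: about 9% risk of a false positive in at least one arm, against the 5% used for sizing; PRAM over time has no key time and no method for repeated scores

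*Combined protocol and SAP*

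**What the plan says.** All references are to the combined protocol and SAP.

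- **Arms and contrasts.** Three arms are randomised in blocks of six (Study summary). Under Statistical analysis: "Outcomes in the two treatment arms of the study (BiPAP and CPAP), will be compared to those in the control group". This makes two contrasts on one shared control.
- **Sizing.** The Sample size calculation states "we would define a significant treatment effect as a 25% reduction in time to PRAM of 3", "with a power of 80% and a 5% chance of a type 1 error". The inputs are ICU times from a pilot study with 10 patients per arm: "BiPAP reduced time in ICU (48+/- 16 hrs vs. 36+/-14 hrs". It arrives at 26 per arm and calls this a rough estimate. The Overview of study design projects at least 30 per arm.
- **Time to the PRAM target (item 2).** "Comparison between treatment and control values will be made using t test". Nothing more is given. The target is written as 3, below 3, or at most 3 in different places; it is called the PRAM target here.
- **PRAM over time (item 1).** "Multiple comparisons over time, between treatment group and control, will be made with the Kruskal-Wallace test with Dunn's posthoc test". Scores are taken every 4 hours (Overview of study design).
- **Drug treatments (item 3).** "Comparisons between control and treated group of repeat measures over time, will be made by analysis of variance with Tukey's post-hoc test".
- **FEV1 (item 4).** "Multiple comparisons between control and treated groups will be made by analysis of variance with Tukey's post-hoc test".

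These four are called the principal end points. None is named primary.

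**The concern.** The plan names a between-arm post-hoc procedure for three of its four principal end points. The one without is the endpoint on which the sample size rests.

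The Study background presents CPAP and BiPAP as two forms of NIV, and both statements of aim (Hypothesis and aims; Overview of study design) ask whether NIV helps. A significant result in either arm would be read as a yes. With two unadjusted tests, the chance of a false yes is higher than for the single comparison used in sizing.

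For PRAM over time, the analysis sentence can be read in two ways. If all arm-by-time cells go into one Kruskal-Wallis test, repeated 4-hourly scores on the same child are treated as independent. If the test is run at each time, there are many looks and no time is fixed in advance as the one on which the conclusion rests. The trial is open, so that choice could be made by someone who knows the allocation.

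**Working it through.** **Inputs.** From the Sample size calculation: control mean 48 h, reduction 25% (0.25 × 48 = 12 h), larger SD 16 h, type 1 error 5%, power 80%. From the Overview of study design: 30 per arm. Assumed, because not stated outright: two-sided tests and equal allocation.

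**1. The plan's own sample size.** n per arm = 2 × [SD × (1.960 + 0.842) / difference]² = 2 × (16 × 2.802 / 12)² = 27.9, so 28. The t-based figure is 29. With the two pilot SDs pooled, √((16² + 14²)/2) = 15.03, the result is 25 (normal) or 26 (t-based). The stated 26 is therefore close to, or equal to, the size for one two-group comparison at the full two-sided 5%. It leaves no room for a second comparison.

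**2. False positives with two tests on a shared control.** With equal arms the two test statistics have correlation 0.5. If neither NIV mode works:

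P(at least one significant) = 0.05 + 0.05 − P(both) = 0.10 − 0.0093 = 0.0907.

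In favour of NIV only: 0.025 + 0.025 − 0.0046 = 0.0454.

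Simulated t tests with a shared control (400,000 trials per setting):

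| No effect in either arm | 26 per arm | 30 per arm |
|---|---|---|
| At least one p<0.05, either direction | 9.1% | 9.1% |
| At least one in favour of NIV | 4.5% | 4.5% |
| Single test, either direction | 5.0% | 5.0% |
| Single test, in favour of NIV | 2.5% | 2.5% |
| Dunnett, either direction | 5.0% | 5.1% |
| Dunnett, in favour of NIV | 2.5% | 2.5% |

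A fixed sequence has the error of its first test, 5.0%. The Dunnett critical values used were 2.256 (26 per arm) and 2.247 (30 per arm).

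**3. Power for 12 h, SD 16 h.**

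| Method | 26 per arm | 30 per arm |
|---|---|---|
| Unadjusted t test, per arm | 75.5% | 81.5% |
| Fixed sequence, first arm | 75.5% | 81.5% |
| Fixed sequence, both claimed if both work | 63% | 71% |
| Dunnett, per arm | 67% | 74% |
| Step-down Dunnett, per arm, both work | – | 79% |
| Step-down Dunnett, only one works | – | 74% |

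In a fixed sequence with BiPAP first, if only CPAP works, CPAP is claimed in about 2.5% of trials instead of about 82%. Keeping 80% per arm with Dunnett would need about 34 per arm (normal approximation, nominal level about 0.027).

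**4. PRAM over time.** No rate is given here. It would depend on the means, the SD, the within-child correlation, the number of times and the reading of the sentence, and the plan gives none of the quantities for scores over time. The point follows from the text: the contrast is named, the time is not, and neither reading of the sentence handles repeated scores on a child within a single pre-stated test.

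**The case against.** The strongest counter-argument is that BiPAP and CPAP are distinct treatments, each compared with control, and that trials with several arms need not adjust across separate questions. The Study background even describes the planned trial in terms of the value of BiPAP alone. Statisticians do differ on this, and on that reading every test keeps 5%. This part stands: the plan uses 5% as an input to a two-group calculation and nowhere calls it joint. A reader might infer that the plan promises a joint 5% and breaks it; the text does not support that. What remains is that both statements of aim pose one NIV question, and the plan does not say which error rate it means.

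A reader might also infer that PRAM over time names no contrast, or that its error is known to be badly inflated. Neither holds. Item 1 names treatment against control, and Dunn's test is a multiple-comparison procedure. The size of any inflation cannot be derived from the documents.

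A third objection is that the gain is limited, because four end points share principal status. As an illustration, assume independent end points and 5% for each of the other three. Then the chance of any false positive falls only from 1 − 0.909 × 0.95³ = 22% to 1 − 0.95⁴ = 18.5%. This is fair, and it bounds what the change achieves. It does not make the looser test on the sizing endpoint preferable.

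**Conclusion.** The point holds for the trial's single NIV question. On time to the PRAM target, the chance of a false positive in at least one arm is about 9%, not the 5% used for sizing. It would be wrong to read the whole 9% as false benefit: in favour of NIV it is 4.5%, against 2.5% for one test. These figures assume two-sided tests, equal arms and no effect of either mode. They cover this one endpoint.

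The power figures are conditional on ICU time from a small pilot standing in for time to the PRAM target (12 h, SD 16 h), and on every child having a value. The plan itself calls its estimate rough.

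For PRAM over time the conclusion is qualitative: no key time is set, and the named test does not suit repeated scores on the same child. The two parts together merit a change to the analysis text before data are analysed.

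**What to change.** **1. Time to the PRAM target.** State that the 5% covers both comparisons with control. Replace the separate t tests by Dunnett's procedure, preferably step-down, or by a fixed sequence with the order written down (for example BiPAP first, since the sizing data are for BiPAP). Restate power at 30 per arm as conditional on the pilot proxy: about 82% for the first arm in a fixed sequence, 74% per arm with Dunnett, 79% with step-down Dunnett if both modes work.

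**2. PRAM over time.** Pre-state one contrast per NIV arm: the difference from control at one named early time, or averaged over one named early window, when most children are still under observation. Adjust for baseline PRAM, which is already scored hourly in the ER. Include all randomised children, with a pre-stated rule for those discharged or withdrawn before that time. Hold 5% over the two contrasts by the same method as in (1), and report other times descriptively. An ordinal repeated-measures model is one option, not a requirement.

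**Cost.** Analysis text and a restated power figure; no new data. Dunnett at the planned 30 per arm falls below the intended 80%, and restoring it would take about 34 per arm. A fixed sequence loses nothing for the first arm but gives up any claim for the second if the first fails.

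**Limit.** This holds 5% within each of these two end points. It does not control error across the four principal end points, which would need one to be named primary.

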## **Research Methods:**

## Overview of study design:

The aim of the study is to determine if the use of NIV, for children admitted to hospital with an acute exacerbation of asthma, reduces their work of breathing, need for adjunctive medication, length of hospital stay, and need for intubation and mechanical ventilation. Study design will be prospective, randomized and controlled. The tightly fitting face mask necessary for NIV makes it impossible to make this a blinded study.

The principal enrollment criteria will be children over 2 years of age presenting to the ER with acute asthma. After diagnosis, all children are treated with standard therapy (systemic steroids plus 3 doses of inhaled salbutamol and 1 dose of inhaled ipratropium over a 1 hour period then hourly salbutamol). The principal decision between discharge track and admission track will be made at 2 hours after first steroid dose. Admission criteria are based on sequential PRAM scores.

After initial asthma treatment and observation in the emergency room, to determine which patients can be discharged home, those who need admission will be asked to join the study, then consented and randomized. There will be three treatment groups:

- BiPAP: standard steroid dose, hourly salbutamol and BiPAP at 15/5 cm H2O by face mask with rate 10 to 15/min, oxygen as needed.
- CPAP: standard steroid dose, hourly salbutamol and 8 to 10 cm H2O constant pressure by face mask, oxygen as needed.
- Conventional therapy: standard steroid dose plus hourly nebulized salbutamol, nebulized ipratropium q 6 hrly, magnesium sulphate 50 mg/kg IV (4 doses q 6 hrly), loading dose of aminophylline 6 mg/kg IV if no progress, oxygen as needed.

All children will be admitted to a small 3 bed respiratory unit. They will be closely monitored and objectively scored every 4 hours using the PRAM asthma clinical severity score (Pediatric Respiratory Assessment Measure)[18]. End points will be: time to reach room air, time to reach PRAM score <3, numbers requiring intubation and mechanical ventilation and medication use. Those children older than 5 or 6 yrs, will also perform lung function tests twice daily. Projected patient enrollment will be at least 30 in each arm. Estimated study duration is 6 months.

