#### Measured Outcomes:

- Length of time to reach a PRAM score of  $\leq 3$
- Time to room air.
- Total medication use per 12 hr period.
- Numbers failing treatment and transferred to ICU.
- Numbers in each group requiring hospital readmission within 48 hours of discharge
- Time to reach FEV1 >80% predicted in those children able to perform PFTs.

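### Item 1 sets no error control across the 4-hourly PRAM times and no rule for scores lost to discharge, ICU transfer or discontinuation; this affects a supporting analysis, not the powered end point

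*Combined protocol and SAP*

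**What the plan says.** The Statistical analysis text, which follows the sample size calculation, says that outcomes in the BiPAP and CPAP arms "will be compared to those in the control group". It then lists four principal end points. The first is change in asthma score over time: "Multiple comparisons over time, between treatment group and control, will be made with the Kruskal-Wallace test", with Dunn's test post hoc. Item 3, on drug treatments, does refer to repeated measures. Item 1 does not.

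Under Overview of study design, children are "objectively scored every 4 hours using the PRAM asthma clinical severity score". The same section says the mask "makes it impossible to make this a blinded study".

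The end-point lists elsewhere are framed differently. The Overview has "End points will be: time to reach room air, time to reach PRAM score" and Measured Outcomes has "Length of time to reach a PRAM score of" 3 or below. Neither list includes change in PRAM over time.

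Three routes by which scores can stop are visible:
- **ICU transfer.** Measured Outcomes counts "Numbers failing treatment and transferred to ICU".
- **Discharge.** It appears in the analysis-related text only as the start of a readmission window: "Numbers in each group requiring hospital readmission within 48 hours of discharge".
- **Discontinuation.** Criteria for study termination ends participation on impending respiratory failure and lists BiPAP intolerance.

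No section says how PRAM is handled after any of these, or whether scoring continues in ICU.

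**The concern.** Kruskal-Wallis compares independent groups. It can validly be applied to one summary per child, or at each time separately. The plan names no summary, so testing at each time is the natural reading. (Treating the times as groups would take repeated scores on one child as independent, which is wrong.) Dunn's test, if its adjusted form is used, handles the arms at one time but not the set of times. In an unblinded trial with no time named in advance, a chance difference at any one of them could be reported as an effect.

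The lost scores are a separate problem. Whether a child is still scored depends on how that child is doing. A faster arm loses its recovered children first, so a comparison among those remaining can understate a real benefit. Loss of the sickest children to ICU could push the comparison either way.

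**Working it through.** **The plan's own figure.** No figure is given for item 1. The sample size uses a 12 h difference (48 vs 36 h), SD 16, 80% power and 5% error: n = 2 × [16 × (1.960 + 0.842) / 12]² = 27.9, so 28 per arm against the stated 26. This is within two patients, and the point does not depend on it.

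**Number of times.** Scoring every 4 h gives 24/4 = 6 times in 24 h and 48/4 = 12 in 48 h. The plan gives no scoring period, so both are assumptions.

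**Error across times.** With an independent 5% test at each time, 1 − 0.95⁶ = 26.5% and 1 − 0.95¹² = 46.0%. Scores on one child are correlated, so these are upper markers. A null simulation used 3 arms × 30, integer scores kept within 0–12 (mean 6, SD 2), first-order autoregressive correlation and 6,000 runs. A finding required Kruskal-Wallis p<0.05 and a Dunn difference from control, adjusted over the three pairs.

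| Times | Lag-1 correlation | Any treatment-vs-control difference | Favouring treatment | Any Kruskal-Wallis p<0.05 |
|---|---|---|---|---|
| 1 | – | 2.7–3.3% | 1.4–1.9% | 4.5–5.4% |
| 6 | 0.9 | 9.6% | 5.1% | 14.9% |
| 6 | 0.7 | 13.4% | 6.7% | 20.9% |
| 6 | 0.5 | 14.9% | 8.0% | 23.9% |
| 12 | 0.9 | 15.3% | 7.9% | 22.9% |
| 12 | 0.7 | 22.9% | 11.8% | 35.5% |
| 12 | 0.5 | 27.2% | 14.9% | 41.3% |

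Simulation error at 15% is √(0.15 × 0.85 / 6000) = 0.5 points.

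**Lost scores.** Recovery times (first reaching PRAM 3) are taken as normal with means 48 and 36 h and SD 16, from the sample size text. Assumed: starting PRAM uniform on 8–10 or 8–12 (the Study summary sets 8 as the entry threshold), a linear fall to 3 at recovery, the same slope on to a floor of 0, and noise SD 0.7–1.5.

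A child is still scored at 36 h if recovery time plus the lag to the end of scoring exceeds 36 h. The expected number out of 30 is 30 × Φ[(mean − 36 + lag)/16]. At lag 0 this gives 30 × Φ(0.75) = 23 control and 30 × Φ(0) = 15 treated children. At 12 h it gives 30 × Φ(1.5) = 28 and 30 × Φ(0.75) = 23. At 24 h it gives 30 × Φ(2.25) = 30 and 30 × Φ(1.5) = 28.

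| Scoring ends | Difference at 36 h (points) | Two-group rank-test power |
|---|---|---|
| Never (all scored) | 1.24–1.43 | 57–73% |
| 24 h after recovery | 1.12–1.30 | 48–65% |
| 12 h after recovery | 0.83–0.97 | 29–45% |
| At recovery | 0.42–0.49 | 10–22% |

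**Baseline PRAM.** The Study summary has PRAM scored hourly in the ER, but no analysis uses it. For time to PRAM 3 with 30 per arm, a covariate correlated r with the outcome reduces the SD to 16 × √(1 − r²). Power for one comparison rises from 81.5% (t test) to 83.0, 85.0, 87.6 and 91.0% at assumed r of 0.2, 0.3, 0.4 and 0.5.

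**The case against.** The strongest reply concerns weight. The sample size and the definition of a worthwhile effect both rest on time to PRAM 3, and change in PRAM over time is missing from both end-point lists. A reader might infer that the trial's main result carries a 15–27% false-positive risk. The documents do not support that: item 2 is a separate test of one value per child. The listing of item 1 under principal end points keeps the gap from being negligible, but this is a supporting analysis.

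A reader might also take it as settled that every time is tested, or that 26–46% is the error rate. The text does not say the first, and the second ignores correlation within a child. The 10–15% and 15–27% also include differences favouring control; false benefit is about half of that.

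On lost scores, it would go too far to say that the plan will hide a real benefit. No discharge criterion is given, so the lag is unknown. At 24 h the loss is mild. The lag-0 case is extreme, because the Overview and item 2 set the target below 3, so scoring would not stop on reaching 3. Bias from ICU transfer has not been quantified, and its direction is open.

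Finally, any replacement involves choices. A window mean asks a different question from change over time, and ranking ICU transfers worst brings in an outcome already counted separately. That is fair. It argues for making the choices openly beforehand, not for leaving them unmade.

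**Conclusion.** The point holds in limited form and should be acted on. Item 1 names no decisive time, no per-child summary, no error control across times and no rule for lost scores. Read as testing at each time, it raises the chance of a spurious treatment-versus-control difference from about 3% to about 10–15% over 24 h or 15–27% over 48 h, and of a spurious benefit to about 5–8% or 8–15%. These figures assume the number of times, the correlation and the adjusted form of Dunn's test, which the plan does not specify.

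Restricting the analysis to children still scored can cut power at 36 h from 57–73% to anywhere between 48–65% and 10–22%, depending on an unstated lag and an assumed trajectory. The method in item 1 does not affect the powered comparison. The unused baseline PRAM is a lesser matter of precision only, and the PRAM 8 entry threshold may limit the gain.

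**What to change.** Replace item 1 with text along these lines:

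> Each child's mean 4-hourly PRAM over the first [24 or 48] h, from the same time origin as item 2, is compared by a rank-based analysis adjusted for the last pre-randomisation PRAM. BiPAP vs control and CPAP vs control are Holm-adjusted at two-sided 5%, with children in the arms as randomised. After any discharge the last score is carried forward; [rule for readmission within the window]. Children transferred to ICU, or discontinued for impending respiratory failure, within the window share the worst rank. A sensitivity analysis uses observed scores only. Scores at each time are shown without p-values. This analysis supports time to PRAM 3.

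The window and the readmission rule must be settled before data are seen. Carry-forward and worst rank are examples; other stated rules would serve. Criteria for study termination should also say that stopping the mask does not end PRAM scoring; this concerns data collection, not treatment. Separately, add the last pre-randomisation PRAM as a covariate for time to PRAM 3.

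**Cost.** The change is to analysis text, plus continued scoring after mask intolerance. The lost-score rules are assumptions, worst rank depends partly on an unblinded transfer decision, and scores outside the window become descriptive.

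In the trajectory model above, with a 12 h benefit in both arms and the clock at randomisation, the 24 h version held family-wise error at 3.7–5.2%. Power for at least one arm, and the share of treated-arm scores carried forward, were:

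| Analysis | Power, no ICU transfer | Power, 10% transfer in every arm | Carried forward |
|---|---|---|---|
| 24 h mean | 54–72% | 39–50% | 0–10% |
| 48 h mean | 51–83% | 57–63% | 5–32% |
| Time to PRAM 3 (Holm; worst rank if transfers) | 85–87% | 66–68% | – |

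The longer window uses later scores but leans more on carry-forward. The lower power than time to PRAM 3 is a further reason to label the analysis supporting.

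### The t test on time to the PRAM target has no rule for children who never reach it, and is biased if such losses differ between arms

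*Combined protocol and SAP*

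**What the plan says.** Time to the PRAM target is the outcome that sizes the trial: "we would define a significant treatment effect as a 25% reduction in time to PRAM of 3". Statistical analysis, item 2, gives one reason for its method, "The value will be measured in hours after starting treatment so the values will be parametric", and then the method: "Comparison between treatment and control values will be made using t test". The documents give no transformation, distribution check, censoring rule or value for a child who does not reach the target.

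Other sections provide for such children:

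- Measured Outcomes lists "Numbers failing treatment and transferred to ICU".
- Overview of study design counts children who need intubation and mechanical ventilation.
- Criteria for study termination ends participation for impending respiratory failure. It also lists failure to tolerate BiPAP, including refusal of the mask.

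The target is written as below 3 in Overview of study design and in item 2, as 3 or below in Measured Outcomes, and as a PRAM of 3 in the sample size section.

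**The concern.** This is a time-to-event outcome. A t test needs a number of hours for each child. For a child whose participation ends before the target is reached, the plan supplies none, so the analyst must drop the child or choose a value. The trial cannot be blinded, so that choice would be made with the arm known.

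Dropping is the natural default, and it is not neutral. Children who go to ICU or stop early are likely to be those who would have recovered slowly, so removing them shortens the mean time in whichever arm loses more of them. Loss can differ by arm by design, because mask intolerance can arise only with a mask. An arm could then look faster because it failed more often.

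**Working it through.** **1. The plan's own figure.** Inputs from Sample size calculation: "they showed BiPAP reduced time in ICU (48+/- 16 hrs vs. 36+/-14 hrs"; the higher SD, 16 h; an effect of 25% of 48 h = 12 h; 80% power; 5% type 1 error (two-sided assumed).

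- n per arm = 2 × SD² × (1.960 + 0.842)² / 12².
- With SD 16: 2 × 256 × 7.85 / 144 = 27.9, so 28.
- With the pooled SD, √((16² + 14²)/2) = 15.03, and the t correction: 26.

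The stated 26 is reproduced within rounding of method. The formula assumes that every child contributes a time.

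**2. Model for the check (assumed).** Times are lognormal with control mean 48 h and SD/mean 16/48 = 0.33, so σ² = ln(1 + 0.33²) = 0.105. There are 30 per arm (the projected enrolment), with times rounded up to the 4-hourly scoring. The probability of not reaching the target is proportional to the child's underlying time cubed, scaled to the stated share. The t test uses only children with a time.

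**3. No true effect on speed, unequal loss.** Nominal chance of a significant result favouring non-invasive ventilation (NIV): 2.5%.

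| Non-reachers, NIV v control | t test on recovered children favours NIV |
|---|---|
| 10% v 5% | about 4% |
| 15% v 5% | about 6% |
| 30% v 5% | about 17% (up to 21% in repeat simulations) |

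At 30% v 5% with SD/mean 0.5 the figure is about 29%. A rank test with non-reachers placed last favours NIV in about 0.1% of trials at 30% v 5% and SD/mean 0.33. A t test given every child's underlying time, as if all had been followed to the target, returns to 2.4%. The error therefore comes from the lost children.

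**4. Limiting case.** Suppose the children lost are exactly the slowest in the NIV arm, with none lost in control (20,000 simulated trials, SD/mean 0.33).

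| Slowest dropped, of 30 | Apparent reduction | Favours NIV |
|---|---|---|
| 1 | 3.1% | 5.7% |
| 2 | 5.3% | 9.9% |
| 3 | 7.3% | 15.4% |
| 6 | 12.3% | 34.4% |

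**5. Power when the effect is real** (48 h to 36 h, SD/mean 0.33 in both arms, 30 per arm).

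- No failures: t test and rank-sum test both about 91%.
- 15% failing in each arm, slower children more often: rank test about 68%, recovered-only t test about 92%.
- 10% failing in each arm, unrelated to speed: 73% and 88%.

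**The case against.** The strongest objection is that the plan does not say lost children will be dropped. General care for all three groups provides for ICU admission on deterioration without saying that scoring stops there, and a child followed to recovery would have a time. That stands for some ICU transfers. It does not cover children whose participation ends under Criteria for study termination, and no section says that scoring continues.

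The failure shares are also unanchored. At a small imbalance the error is modest, about 4% instead of 2.5%, and 30% v 5% is an extreme case. This stands too, which is why the range is shown.

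A reader might infer two further faults that the documents do not support.

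- **Skew costs the t test power.** At the document's own SD/mean of 0.33 the t test and the rank test are equal, and skew alone leaves the type I error at 4.2% to 4.8%. Holding SD at 16 h in both arms does give 81% v 89% in favour of the rank test. However, the lognormal medians are then 48/√1.111 = 45.5 h and 36/√1.198 = 32.9 h, a reduction of about 28% rather than 25%, so part of that gain comes from the parameters.
- **Children sent home at a PRAM of 3 can never reach the target.** No discharge rule is stated, and the Appendix only lists severity bands. This group would arise only from the <3 / ≤3 inconsistency.

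Finally, ranking failures last changes the question to one that combines speed with failure. In the 30% v 5% scenario the rank test favours control in about 15% of trials. That reflects a real excess of failures, but it should be stated.

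**Conclusion.** The concern holds on validity. The only reason given for the t test is not a reason, and the comparison that sizes the trial has no rule for children whom the plan itself expects. If they are dropped and losses differ by arm, the chance of falsely favouring NIV rises from 2.5% to about 4%, 6% or 17% at 10%, 15% or 30% non-reachers against 5% in control. These figures rest on lognormal times, SD/mean 0.33, 30 per arm and slower children failing more often. The documents give neither failure rates nor the shape of the distribution. With nearly complete recovery in all arms the problem is small. The findings do not show that the t test is the less powerful choice at the plan's own figures.

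**What to change.** In Statistical analysis, item 2:

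1. Delete the clause that infers a parametric variable from its unit.
2. Analyse all randomised children in their allocated arm.
3. Keep recording PRAM to the target, where possible, after a child stops the device or moves to ICU.
4. Replace the t test with a rank test for censored data (for example Gehan-Wilcoxon) of each NIV arm against control. Children with ICU transfer or intubation who do not reach the target rank after all recovered children. Children who leave for other reasons without reaching it are censored at their last score, so that a nearly recovered child is not tied with an ICU transfer.
5. Report the proportion recovered over time in each arm and, as support, a ratio of times to read against the 25% target.
6. Write the target one way. Overview of study design, Measured Outcomes, the sample size section and item 2 must be reconciled.

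Cost: mostly wording, plus continued scoring of a few children; item 1 already uses rank methods. Censoring other leavers assumes that their leaving is unrelated to recovery, which is a further reason for step 3. The main price is power: about 68% against 92% for the recovered-only t test, which answers a different question, when 15% fail in both arms. The sample size section should therefore say that its 80% power applies only if nearly all children reach the target.
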